#### 9.1.5 Unscheduled Visit(s)

Additional visits may be scheduled, as necessary, to ensure the safety and well-being of subjects. All additional examinations should be fully documented in the source documents and on Unscheduled Visit CRFs, as appropriate. Visits intended to fulfill scheduled visit requirements that fall outside the designated scheduled visit window are not Unscheduled Visits. In these cases, the visit data will be collected and transcribed to the appropriate scheduled visit CRF.

If a subject is seen for multiple visits during a given visit timeframe, the data from the visit that is intended to meet the protocol requirements for the scheduled visit will be captured on the visit CRF. Where such a determination cannot be made, the first visit within the scheduled visit interval will be used for completion of the protocol required scheduled visit CRF. Data from any additional visits within a scheduled visit interval will be captured on an Unscheduled Visit CRF.

#### 9.1.6 Missed Visit(s)

If a subject misses any scheduled follow-up visit and cannot be seen prior to the start of the visit range for the next scheduled follow-up visit, the visit is considered missed.

# 9.2 Post-Study Follow-Up

If a subject requires further follow-up upon discontinuation or completion of the study, the Investigator should schedule post-study follow-up visits, as necessary. Refer to Section 10.4.5 for follow-up of AEs following study exit.

# 9.3 Study Completion

The Sponsor or its representative will notify the Investigator and/or the IRB/IEC, as applicable, to inform them when the study is complete. The study will be considered complete when all enrolled subjects either have completed study visits through Visit 4 or have been discontinued from the study prior to Visit 4 for any reason.

#### 9.3.1 Early Study Termination

If during the study it becomes evident to the Sponsor that the study should be stopped prematurely, the study will be terminated, and appropriate notification will be given to the Investigator(s), IRB/IEC, and HC and/or local Health Authority, as applicable. The Sponsor or its representative will instruct the Investigators to stop enrolling and dispensing study materials/treatment and to arrange for study closeout at each site as appropriate. Masking of treatment assignments will continue until the Sponsor unmasks the study.

# 10 Primary and Secondary Safety and Performance Variables

### 10.1 Evaluation of Safety

The primary safety variables will be:

- The incidence of all serious adverse events, including secondary surgical interventions (SSIs) related to the optical properties of the IOL, through Post-Operative Visit 4 (Day 120 to Day 180 after second eye IOL implantation)
- The cumulative rate of secondary surgical interventions due to the optical properties of the lens, through Post-Operative Visit 4 (Day 120 to Day 180 after second eye IOL implantation)
- The incidence of adverse events, through Post-Operative Visit 4 (Day 120 to Day 180 after second eye IOL implantation), compared to ISO Safety and Performance Endpoint (SPE) rates as defined in ISO 11979-7:2018 Annex E

The secondary safety variables will be:

(Data for these safety variables will be summarized with descriptive statistics lacking hypothesis)

• The incidence of subjects experiencing at least one severe visual disturbance, defined as the highest grade of severity or bothersomeness (separately) reported by subjects

- using the Quality of Vision (QoV) questionnaire through Post-Operative Visit 4 (Day 120 to Day 180 after second eye IOL implantation).
- Photopic contrast sensitivity with glare at Post-Operative Visit 4 (Day 120 to Day 180 after second eye IOL implantation).
- Mesopic contrast sensitivity with glare at Post-Operative Visit 4 (Day 120 to Day 180 after second eye IOL implantation).
- Mesopic contrast sensitivity without glare at Post-Operative Visit 4 (Day 120 to Day 180 after second eye IOL implantation).

#### **10.2** Evaluation of Performance

The primary performance variables will be:

- Photopic uncorrected distance visual acuity (UDVA) for first implanted eyes at 4 m at Post-Operative Visit 4 (Day 120 to Day 180 after second eye IOL implantation).
- Photopic uncorrected near visual acuity (UNVA) for first implanted eyes at 40 cm at Post-Operative Visit 4 (Day 120 to Day 180 after second eye IOL implantation).
- Photopic uncorrected intermediate visual acuity (UIVA) for first implanted eyes at 66 cm at Post-Operative Visit 4 (Day 120 to Day 180 after second eye IOL implantation).

#### Secondary Performance Variables:

- IOL rotation for all trifocal eyes at Post-Operative Visit 4 (Day 120 to Day 180 after second eye IOL implantation).
- Change from baseline (preoperative) in uncorrected photopic near visual acuity (UNVA) at 40 cm for first implanted eyes to Post-Operative Visit 4 (Day 120 to Day 180 after second eye IOL implantation).
- Change from baseline (preoperative) in uncorrected photopic intermediate visual acuity (UIVA) at 66 cm for first implanted eyes to Post-Operative Visit 4 (Day 120 to Day 180 after second eye IOL implantation).

The supportive performance variables will be:

(Data for these performance endpoints will be summarized by treatment group with descriptive statistics lacking hypothesis)

- Photopic distance-corrected visual acuity (CDVA, DCNVA, and DCIVA) for first implanted eyes at Post-Operative Visit 4 (Day 120 to Day 180 after second eye IOL implantation).
- Photopic and mesopic binocular uncorrected near and intermediate visual acuity (UNVA and UIVA) at 40 cm and 66 cm, respectively, at Post-Operative Visit 4 (Day 120 to Day 180 after second eye IOL implantation).
- Binocular CDVA defocus curves from +1.50 D to -3.50 D.

#### 10.3 Risk Assessment, Risk Mitigation, and Anticipated Benefit

The model MX60EFH IOL has similar material, mechanical, and biocompatibility properties to the FDA-approved model MX60 and optically equivalent MX60E monofocal IOLs that have

been shown to be safe for implantation in humans.  Reduced contrast sensitivity and increased visual disturbances, such as glare and halo, are known to occur more frequently with multifocal IOLs and will be evaluated in this study through the patient reported outcome (PRO) Quality of Vision questionnaire and a contrast sensitivity sub-study.

The known risks of multifocal IOL implantation that exist in addition to the risks of monofocal IOLs include the following:

- Under scotopic and mesopic conditions, the patient has reduced contrast sensitivity,
- There is an increased risk of post-operative photic effects such as halos and glare.

Studies on other adverse perception effects following multifocal IOL implantation, such as stereo acuity disturbances and aniseikonia, have generally indicated an acceptable performance range. 

Multifocal IOLs achieve correction of presbyopia by dividing incoming light into two or more focal points. Patient selection and counselling are particularly important with these IOLs. There may be a symptomatic reduction in the quality of distance vision, particularly if other ocular pathology is present. Therefore, the candidacy of patients with amblyopia or abnormalities of the cornea, optic disc, and macula for a multifocal IOL must be carefully considered. Although uncommon, explantation of multifocal IOLs may become necessary if optical side effects are intolerable. 

A Cochrane systematic review concluded that multifocal IOLs are effective at improving near vision relative to monofocal IOLs, although there is uncertainty as to the size of the effect. Whether that improvement outweighs the adverse effects of multifocal IOLs, such as glare and haloes, will vary between people. Motivation to achieve spectacle independence is likely to be a deciding factor. 

Mitigation of the risks related to undesirable optical phenomena of multifocal IOLs includes exclusion of potential subjects with ocular pathology which may limit the quality of postoperative vision such as abnormalities of the cornea, lens capsule-zonular apparatus and macula, as well as thorough discussion of the characteristics of dysphotopsia such as halos, glare and reduced contrast sensitivity during the informed consent process. As noted above, candidacy of patients for multifocal IOL implantation depends not only on objective findings during a complete ophthalmologic examination, but also on patients' motivation to achieve spectacle independence. The risks and benefits must be weighed on an individual basis by the investigator in consultation with each potential subject. Ensuring the subject's thorough understanding of the optical side-effects of multifocal IOLs and ascertaining the subject's degree of enthusiasm for spectacle independence form the basis of informed consent and risk mitigation.

Despite concern about risks of multifocal IOL implantation, the value of conducting a clinical study to support approval of a multifocal IOL is substantial in terms of providing another IOL option to increase potential patient satisfaction and improved near and intermediate vision while maintaining good distance vision. Prior studies of multifocal IOLs have shown a high degree of patient satisfaction, both in absolute terms and compared to monofocal IOLs, improved near vision, and a very low rate of IOL explantation due to optical side-effects. 31-34

These results indicate that application of the principles of informed consent and patient selection to the risk of dysphotopsia and contrast sensitivity reduction will provide greater

benefit than risk and justify the enrollment of subjects in this study of a multifocal IOL. Specifically, we have done a design risk analysis for the enVista MX60EFH trifocal IOL and have concluded no mitigations is needed beyond that stated in the Section.

An anticipated benefit which a subject may derive from participation in this study is an improvement of their vision as a result of the removal of their cataracts. If the subject is randomized to receive the enVista MX60E monofocal IOL, it is expected they will have improvement in their distance vision and would then require the use of corrective lenses (such as glasses or contact lenses) for near and intermediate vision. If a subject is randomized to receive the enVista MX60EFH trifocal IOL, they may have improvement in their near and intermediate vision while maintaining comparable distance visual acuity to a monofocal IOL, allowing them to be able to read, use a computer, and watch television without reading glasses or bifocals.

Further discussion of potential or actual risks during cataract surgery and with the use of multifocal or monofocal enVista IOLs as well as IOL injectors to be used in this study can also be found and should be accessed in the study Investigator's Brochure and/or the relevant IOL Directions for Use (DFU) provided by the Sponsor as manufacturer. Of note, the enVista IOL medical devices according to the Design Risk Analysis (DRA) are not susceptible to environmental influences or concomitant medical treatments once implanted in a patient's eye.

#### **10.4** Adverse Events

Each subject eye treated must be examined for the presence/absence of adverse events at all visits, whether scheduled or not. If an adverse event (AE) occurs, the first concern will be the safety and welfare of the subject; treatment should be provided as appropriate for the event.

#### **10.4.1** Adverse Events Definitions

For the purposes of this study, adverse events include: all ocular AEs; all ocular and non-ocular serious adverse events (SAEs); adverse device effects (ADEs); and serious adverse device effects (SADEs). Non-ocular adverse events other than non-ocular SAEs will not be collected because of their lack of influence on assessing safety of the Test and Control IOLs. AEs, SAEs, ADEs and SADEs are defined as follows.

An adverse event (AE) is any untoward medical occurrence, unintended disease or injury, or untoward clinical sign (including abnormal laboratory finding) in a subject, user or other persons, whether or not related to the investigational medical device. This definition includes events related to the medical device or procedures involved. For users or other persons, this definition is restricted to events related to the study device.

A Serious Adverse Event (SAE) is an AE that leads to:

- death
- a serious deterioration in the health of the subject that either results in:
  - o a life-threatening illness or injury, or
  - o a permanent impairment of a body structure or body function (e.g., blindness), or
  - o in-patient or prolonged hospitalization, or
  - o a potentially vision-threatening condition, or

- o medical or surgical intervention to prevent life- or vision-threatening illness or injury or permanent impairment to a body structure or a body function
- fetal distress, fetal death, or a congenital abnormality or birth defect

Planned hospitalization for a pre-existing condition will not be considered a serious adverse

An Adverse Device Effects (ADE) is any adverse event related to the use of an investigational medical device or an approved medical device used as a comparator. This definition includes any events resulting from insufficient or inadequate instructions for use, deployment, implantation, installation or operation, or any malfunction of the investigational medical device. This definition also includes any event resulting from device malfunction, use error, inadequate labeling, or from intentional misuse of the investigational medical device.

A Serious Adverse Device Effect (SADE) is any ADE which also meets any of the serious criteria for SAEs.

Anticipated AEs associated with cataract surgery and/or premium IOL implantation that might reasonably be expected to occur in this study, however rare, are listed below and include, but are not limited to, the following:

Anterior capsule tear

Anterior uveitis (including iritis and iridocyclitis) \*

Capsular block syndrome

Choroidal detachment/hemorrhage

Corneal edema \*

Cystoid macular edema (CME) \*

Difficulty with tasks in dim light resulting in secondary surgical intervention\*

Elevated IOP\*

Endophthalmitis (intraocular inflammation requiring vitreous tap and use of intraocular antibiotics)

Events resulting in unplanned secondary surgical intervention other than paracentesis to relieve pressure prior to 1 week postoperative or Nd:YAG capsulotomy

Flat anterior chamber

Hyphema

Hypopyon

Incorrect IOL power resulting in secondary surgical intervention \*

Increased glare or halos

Infectious keratitis

IOL damage resulting in secondary surgical intervention \*

IOL decentration or tilt \*

Iris or pupil damage

Loss of BCVA\*

Mechanical pupillary block (A shallowing of the peripheral and/or central anterior chamber with or without elevation of IOP by obstruction of the flow of aqueous humor from the posterior chamber through the pupil to the anterior chamber). This may be induced by the crystalline lens, vitreous face, or implanted devices.)

Multiple (or "ghost") images other than increased glare or halos

Pain \*

Posterior capsular rupture

Progression or onset of diabetic retinopathy

Progression or onset of macular degeneration

Reduced contrast sensitivity

Retained lens material

Retinal detachment (partial or complete RD associated with retinal tear)

Secondary IOL intervention (reposition, exchange, or removal) for any reason \*

Synechiae formation

Undesirable optical phenomena resulting in secondary surgical intervention

Thermal injury (phaco burn)

Toxic anterior segment syndrome (TASS) (An acute, noninfectious inflammation of the anterior segment of the eye that develops within 24 to 48 hours after surgery and is characterized by corneal edema and accumulation of white cells in the anterior chamber of the eye)

Vitreous prolapse

Wound leak (positive Seidel)

- \* These events may be considered normal or expected events after cataract surgery and only need to be reported as AEs/SAEs if present as specified below:
  - Iritis/cells/flare characterized by grade 1+ cells or greater using SUN criteria if persistent for greater than 3 months after surgery, or relapses in less than 3 months after discontinuation of therapy, or the subject is maintained on therapy for more than 3 months to control inflammation
  - Corneal or corneal wound edema resulting in CDVA of ≤20/40 at Visit 3A or later in the first implanted eye or at Visit 3B or later in the second implanted eye, or any persistent corneal or corneal wound edema present at Visit 4
  - Cystoid macular edema diagnosed by clinical exam and adjunct testing (eg. OCT, FA or other method), resulting in CDVA of  $\leq$  20/40 at Visit 3 or later
  - Elevation of IOP by ≥10 mmHg above baseline (pre-operative) to a minimum of 25 mmHg after Visit 1A in the first implanted eye or after Visit 1B in the second implanted eye, or elevated IOP requiring treatment if present at Visit 4
  - Postoperative refractive error > 1.0 D different from predicted, and not due to calculation or other use error
  - Crack, breakage or deformity of IOL haptic or optic resulting in secondary surgical intervention

- IOL decentration or tilt likely to affect visual outcome and resulting in secondary intervention
- Monocular CDVA decrease of equal to or greater than 2 lines (≥10 letters) from any previous visit not secondary to any underlying condition, or any monocular CDVA decrease from any previous visit of greater than 2 lines if persistent to the subject's last visit in the study.
- Pain, per subjective patient reporting, graded as  $\geq 4$  on the standardized pain rating scale (from 0 to 10)
- Mild superficial punctate keratitis (SPK) present at Visit 3A or later in the first implanted eye or at Visit 3B or later in the second implanted eye, or moderate, severe, or very severe SPK at any post-operative visit (note: if SPK is present pre-operatively, adverse event must be reported only if there is a worsening)

Note: Posterior capsular opacification (PCO) is NOT to be reported as an AE unless the Investigator treats PCO with Nd:YAG laser exposure.

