#### 10.4.3 Evaluations

When evaluating AEs, the Investigator must determine if the event is serious or non-serious (refer to Section 10.4.1 for criteria), assess the severity of symptoms, and determine the relationship of the event to the device, using the following guidelines:

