# 11.4.1.2 Secondary Surgical Interventions Related to the Optical Properties of the IOL

Secondary surgical interventions related to the optical properties of the IOL will be defined as IOL explantation, replacement, or repositioning due to subject intolerance of visual symptoms not adequately improved by spectacle correction. The investigators will apply this definition to classify each secondary surgical intervention as either related to the optical properties of the IOL or not related to the optical properties of the IOL.

Each eye will be classified as either having undergone a secondary surgical intervention related to the optical properties of the IOL or not having undergone such an intervention. Missing data will not be imputed. Secondary surgical interventions related to the optical properties of the IOL will be summarized categorically (Yes, No) by actual treatment received for Safety Set subjects in a table. Secondary surgical interventions will be further subcategorized and summarized categorically as Exchange, Removal, Repositioning, or Other.

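### The first primary safety variable includes optical secondary surgical interventions, but the SAE criteria do not clearly make them serious and the analysis counts only SAEs

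*Combined protocol and SAP*

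**What the plan says.** The synopsis, Section 5.1.1 and Section 10.1 all give the first primary safety variable as "The incidence of all serious adverse events, including secondary surgical interventions (SSIs) related to the optical properties of the IOL", through Visit 4.

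Section 11.4.1.2 defines an optical SSI as "IOL explantation, replacement, or repositioning due to subject intolerance of visual symptoms not adequately improved by spectacle correction" and has the investigators classify every SSI as optical or not.

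Section 10.4.1 sets the criteria for an SAE. Apart from death and fetal or congenital outcomes, every criterion sits under "a serious deterioration in the health of the subject that either results in". The one that concerns surgery reads "medical or surgical intervention to prevent life- or vision-threatening illness or injury or permanent impairment to a body structure or a body function". SSIs are not named there.

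Under Section 10.4.3, "the Investigator must determine if the event is serious or non-serious (refer to Section 10.4.1 for criteria").

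Section 11.4.1.1, like the synopsis, takes as its numerator the Safety Set eyes with one or more SAEs, each eye counted once, by treatment received.

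**The concern.** The endpoint definition includes optical SSIs, and the analysis rule never mentions them. They reach the first endpoint only if the investigator grades them serious, under criteria that were not written with them in mind. Two sites could grade the same lens exchange differently and both be following the protocol.

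This matters because it is a primary safety variable and the event is specific to this class of lens. Section 10.3 acknowledges that multifocal lenses occasionally have to be explanted when their optical side effects cannot be tolerated. Any omission would therefore be expected to fall mainly on the Test arm and lower its rate. Under Section 7.2 the implanting investigator knows the assignment, so grading could also differ by arm.

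The same grading decides expedited reporting. In Tables 1 and 2 and Sections 10.4.4.2 and 10.4.4.3, serious events go to the sponsor within 48 hours and every serious device effect is a Mandatory Problem, due at Health Canada within 72 hours. A non-serious ocular event goes on the CRF only, even if device-related.

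**Working it through.** This is mainly a comparison of text. The plan states no figure for this endpoint that could be reproduced.

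**Step 1: a test case.** Take an outpatient lens exchange for intolerable halos, not relieved by spectacles, in an eye with good acuity.
- *Section 11.4.1.2:* it is an optical SSI. That definition asks for no threat to vision and no permanent impairment.
- *Sections 5.1.1 and 10.1:* it belongs in the first primary safety variable.
- *Section 10.4.1:* there is no death, threat to life, hospitalisation or fetal outcome. Whether there is a serious deterioration in health, a potentially vision-threatening condition, or surgery to prevent permanent impairment is a matter of judgement.
- *Section 11.4.1.1:* the eye is counted if the judgement is serious and is not counted otherwise, unless it has another SAE.

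**Step 2: does the anticipated-event list settle it?** It does not. "Undesirable optical phenomena resulting in secondary surgical intervention" is listed as an anticipated adverse event and is not designated serious. "Secondary IOL intervention (reposition, exchange, or removal) for any reason" is also listed, with an asterisk that limits reporting to the circumstances specified beneath the list. No specification for that item follows.

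**Step 3: effect per eye.** The denominator in Section 11.4.1.1 is all implanted eyes. Section 11.2.3 gives 100/(1 − 0.1) = 111.1, stated as 112 Test subjects, and 50/(1 − 0.1) = 55.6, stated as 56 Control subjects. With both eyes implanted, that is 2 × 112 = 224 Test eyes and 2 × 56 = 112 Control eyes, as in the synopsis.

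If k eyes have an optical SSI graded non-serious and no other SAE, the rate falls by k divided by the number of eyes:
- one Test eye: 1/224 = 0.45 points
- both eyes of one Test subject: 2/224 = 0.89 points
- one Control eye: 1/112 = 0.89 points

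The documents give no optical-SSI rate and no basis for the share graded non-serious, so k cannot be estimated.

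**The case against.** Four replies carry weight.

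- **The endpoint wording may itself settle the matter.** Listing optical SSIs within the SAE variable can be read as treating every one as an SAE, in which case Section 11.4.1.1 counts them. That reading is reasonable. However, Section 10.4.3 sends the investigator to Section 10.4.1 and not to the endpoint definition, so nothing guarantees that it will be applied.
- **An investigator could grade the event serious under Section 10.4.1.** Surgery for symptoms that spectacles do not relieve can be argued to prevent permanent impairment of visual function. This stands. A reader might infer that the criteria exclude optical SSIs and that sites will record them as non-serious. The text supports only that they may.
- **The events are counted elsewhere.** The second primary safety variable counts optical SSIs by eye whatever their seriousness. This stands in full.
- **Nothing is tested.** Section 11.1.1.1 attaches no hypothesis to this endpoint, and Section 11.4 rests overall success on endpoints with success criteria. This also stands. It limits the weight of the point but does not remove the inconsistency.

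A reader might also see a second contradiction in Section 11.4.1.2, where SSIs are to be "subcategorized and summarized categorically as Exchange, Removal, Repositioning, or Other" although the optical definition names only explantation, replacement and repositioning. The documents do not support that. The sentence speaks of SSIs without restricting it to optical ones, so the last category can hold other procedures. There is no ground here for widening the optical-SSI definition.

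**Conclusion.** The concern holds as an inconsistency between a primary safety variable and the rule that estimates it. As written, the plan can produce a first-endpoint rate that omits events its own definition includes, depending on how each site reads seriousness.

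The size is 0.45 percentage points per omitted Test eye. This assumes the planned 224 implanted Test eyes and no other SAE in the affected eye. A reader might multiply this by a guessed SSI rate to get a number of missing eyes. The documents do not support such a total, and Section 10.3 describes explantation for optical reasons as uncommon.

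Nor does it follow that the optical safety signal is lost, or that a conclusion of the trial is at risk. The second primary endpoint keeps these eyes, and no alpha, power or success criterion changes. The correction is worth making because it concerns a primary safety variable and costs little.

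**What to change.** 1. In Section 11.4.1.1 and the matching synopsis text, derive the numerator as eyes with at least one SAE or at least one SSI classified under Section 11.4.1.2 as related to the optical properties of the lens, whatever its seriousness flag. Count each eye once.
2. Show the SAE-only count beside it, so that events graded non-serious are not hidden in a rate labelled as serious.
3. Reconcile Sections 5.1.1 and 10.1 with Section 10.4.1 on whether an optical SSI is an SAE. Changing the derivation alone would leave expedited reporting dependent on the inconsistent grading. Which way to settle this is for the sponsor to decide.
4. Carry the derivation into the SAP, to which Section 11.4 defers further detail.

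The cost is a few lines of derivation text, one extra table row and one protocol clarification. Section 11.4.1.2 already has investigators classify each SSI, so no new data or visits are needed. The downside is that the reported Test rate may be slightly higher.

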#### 10.4.2 Identification and Collection

Identification and collection of an AE begins after informed consent has been obtained and documented. Standard sources of identifying AEs include:

- direct observation by the Investigator
- asking of the study participant a non-specific question (e.g., "Have you had any problems since the last visit?")
- unsolicited volunteering of information by the study participant (e.g., "Doctor, I have had blurred vision since I started using this lens.")
- laboratory or test results that meet protocol requirements for classification as an AE

Specific to this protocol, ocular AEs in the study eye(s) and all SAEs (ocular and non-ocular) observed or elicited by the Investigator, reported by the subject, or resulting from a test result, etc., occurring during the clinical investigation must be reported in the CRF for randomized subjects. For screen failures, AEs are recorded in the source data only, but not in the CRF. Note: The expedited reporting of SAEs with enrolled subjects as described below also applies for screen failures. During the study, the Investigator should treat the study subject as appropriate to ensure his/her safety and welfare. Refer to Section 10.4.5 for additional information pertaining to ongoing AEs at subject exit.

Pre-existing conditions will not be considered AEs but will be collected at the Preoperative Visit as medical history. A worsening of a pre-existing condition during the study should be documented as an AE and evaluated accordingly.

Hospitalizations for admission without a medical AE should be captured as a serious AE until the cause of hospitalization can be identified. However, the following reports of hospitalization without a medical AE should not be considered either serious or an AE:

- Admission for treatment of a pre-existing condition not associated with the development of a new AE or with worsening of the pre-existing condition (e.g., for work-up of persistent pretreatment lab abnormality)
- Social admission (e.g., subject has no place to sleep)
- Administrative admission (e.g., for yearly physical exam)
- Optional admission not associated with a precipitating medical AE (e.g., for elective cosmetic surgery)

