#### 11.4.1.3 ISO Grid Adverse Events

Cumulative and persistent ISO grid AEs will be summarized categorically for all Test group eyes of the Safety Set by treatment. Subjects will be analyzed according to treatment received.

The numerator for each cumulative AE will be the number of all implanted Test group eyes reporting the AE at least once after surgery. The denominator for cumulative AEs will be the number of all implanted Test group eyes.

The numerator for each persistent AE will be the number of all implanted Test group eyes with the event at Visit 4 (Day 120 to Day 180 after second eye IOL implantation). The denominator for persistent AEs will be the number of all implanted Test group eyes present at Visit 4 (Day 120 to Day 180 after second eye IOL implantation).

For each ISO grid AE, a one-sided exact binomial test comparing the proportion of Test group eyes with the AE to the relevant control rate will be completed. If the resulting p-value is less than or equal to 0.05, then the null hypothesis will be rejected. If none of the null hypotheses are rejected, then the test lens will be statistically successful in these endpoints.

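### The starred-event reporting thresholds in Section 10.4.1 extend to SAEs, in conflict with the SAE definition and reporting rules, and leave a gap for cystoid macular edema at Visit 4

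*Combined protocol and SAP*

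**What the plan says.** Section 10.4.1 defines a serious adverse event (SAE) by its consequence. One entry in the list reads "a potentially vision-threatening condition, or" and the next covers intervention to prevent sight-threatening or lasting harm. Neither depends on visit, duration or acuity.

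The same section then lists anticipated events and stars some of them as possibly normal after cataract surgery. The starred events "only need to be reported as AEs/SAEs if present as specified below". Among the specifications:

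- Iritis counts "if persistent for greater than 3 months after surgery", or on early relapse or prolonged therapy.
- Corneal edema: "Corneal or corneal wound edema resulting in CDVA of ≤20/40 at Visit 3A or later in the first implanted eye" (Visit 3B for the second eye), "or any persistent corneal or corneal wound edema present at Visit 4".
- Cystoid macular edema (CME): "Cystoid macular edema diagnosed by clinical exam and adjunct testing (eg. OCT, FA or other method), resulting in CDVA of" 20/40 or worse, at Visit 3 or later. The text does not say 3A or 3B.
- Raised IOP counts if found after Visit 1A or 1B, or if it needs treatment at Visit 4.

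Section 10.4.2 requires CRF reporting, for randomized subjects, of "ocular AEs in the study eye(s) and all SAEs (ocular and non-ocular) observed or elicited by the Investigator". Section 10.4.4.2 requires any SAE to go to the sponsor, within 48 hours.

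The first primary safety variable (Section 5.1.1) is the incidence of all SAEs through Visit 4. For the third, Section 11.4.1.3 defines the cumulative numerator as "the number of all implanted Test group eyes reporting the AE at least once after surgery". The persistent numerator is the eyes that have the event at Visit 4.

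**The concern.** The starred notes name SAEs as well as AEs. Read literally, they let a site leave out an event that the SAE definition would capture, because it came too early or did not reduce acuity far enough. The general rules say the opposite, and the protocol does not rank the two.

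Two things are at stake. The first is the expedited SAE report, which matters whatever the statistics. The second is the count behind the first primary safety endpoint, which would be too low if sites followed the starred notes.

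The CME line raises a second, separate question. It has no counterpart to the Visit 4 clause given to corneal edema, so a case that Section 11.4.1.3 appears to count as persistent may have no AE record.

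**Working it through.** The plan gives no figure on this point, so the check sets the texts side by side.

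**Step 1: what each threshold leaves out.**

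| Starred event | Reportable under the starred notes | Left outside | Limit in the SAE definition |
|---|---|---|---|
| Raised IOP | Rise of at least 10 mmHg to at least 25 mmHg after Visit 1A/1B, or treated at Visit 4 | A rise at the Day 1-2 visit that later settles | None |
| Corneal edema | CDVA 20/40 or worse from Visit 3A/3B, or any persistent edema at Visit 4 | Edema before Visit 3 that clears | None |
| CME | CDVA 20/40 or worse at Visit 3 or later | CME that clears before Visit 3; CME at any visit, including Visit 4, with better acuity | None |

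**Step 2: does another entry catch the early pressure rise?** The unstarred entry for unplanned secondary surgical intervention could do so, but it exempts paracentesis to relieve pressure in the first week. A Day 1-2 rise treated that way can fall outside both entries, even if the investigator would judge it to meet the SAE criteria.

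**Step 3: do the general rules settle it?** Sections 10.4.2 and 10.4.4.2 point towards reporting. However, Section 10.4.1 defines an SAE as a kind of AE, and Section 10.4.2 lists among its AE sources test results that meet the protocol's requirements for an AE. Both lead back to the starred thresholds. A site told that an event is expected may never classify it as an AE, and so never reach the SAE question.

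**Step 4: timing of the CME line.** Visit 3A is Day 30 to 60 after the first surgery. Visit 3B is Day 30 to 60 after the second, which takes place 7 to 30 days after the first. Counted from the first surgery, Visit 3B therefore falls between Day 30 + 7 = 37 and Day 60 + 30 = 90. For a first eye, the start of the CME reporting period is Day 30-60 or Day 37-90, depending on which visit is meant. The corneal edema line avoids this by naming 3A and 3B.

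**Step 5: CME at Visit 4.** Suppose an eye has CME at Visit 4 and CDVA better than 20/40. The CME line does not require a report. The CDVA-loss line may not help: one branch excludes loss secondary to an underlying condition, and the other needs a loss of more than 2 lines persisting to the last visit. Section 11.4.1.3 sets no acuity limit for a persistent event. Corneal edema in the same position is reportable.

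**Step 6: direction for the grid test.** Section 11.4.1.3 compares Test eyes with a fixed historical rate, and success means that no null hypothesis is rejected. Under-recording relative to the definition behind the historical rate would favour success. Whether there is such a shortfall cannot be determined here, because the Annex E event definitions are not reproduced.

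**The case against.** The strongest reply is that the starred notes are permissive. They say what needs to be reported and forbid nothing, while Sections 10.4.2 and 10.4.4.2 and Table 2 are mandatory for every SAE. This stands as far as it goes. A reader might infer that serious early events are never counted, or that the starred notes override the seriousness criteria. The documents do not support either reading; they support a conflict with no stated order of precedence.

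A reader might also infer that severe iritis of every kind escapes. It does not: endophthalmitis, hypopyon, toxic anterior segment syndrome and synechiae are unstarred and carry no threshold. Retinal detachment, pupillary block and infectious keratitis are also unstarred. The IOP exemption for a qualifying rise covers only the first postoperative visit.

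On the grid test, three objections stand. Annex E may define its events with similar thresholds, or may not list CME as assumed here; either would shrink or remove the mismatch. The persistent numerator refers to eyes with the event, so it might be taken from examination data and not from AE reports. And the Visit 4 fundus examination is done only if clinically indicated, which is a separate detection limit that wording on reporting does not cure.

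Finally, the first safety endpoint is descriptive (Section 11.1.1.1). Under-reporting would bias the estimate but could not turn a failed test into a success.

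**Conclusion.** The point holds as two wording defects. First, extending the starred thresholds to SAEs conflicts with the SAE definition and with the reporting rules in Sections 10.4.2 and 10.4.4.2, and the passages must be reconciled. The exposure is limited to starred events that meet the SAE criteria but miss a threshold. It affects the first primary safety endpoint and the 48-hour report. This part needs no outside source.

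Second, CME present at Visit 4 with CDVA better than 20/40 need not enter the AE record, and the Visit 3 reference is ambiguous. Whether this biases the third primary safety endpoint depends on Annex E.

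No magnitude can be given. A reader might be tempted to work out how far the exact binomial test would lose its ability to flag an excess, but that needs the historical rates and the share of events left unreported, and the documents give neither.

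**What to change.** - **(a) Section 10.4.1, starred note.** Replace *AEs/SAEs* with *non-serious AEs*, and state that the starred thresholds never override the SAE criteria or the reporting rules in Sections 10.4.2 and 10.4.4.2.
- **(b) Section 10.4.1, CME line.** Add a clause making any CME present at Visit 4 reportable, and name Visits 3A and 3B as the corneal edema line does.
- **(c) Section 11.4.1.3.** State that each grid event is counted by its Annex E definition and not by the starred thresholds, and check that the CRF captures what that definition needs. Do not go further and count every observed event in a grid category whatever its definition. If the historical rate rests on a narrower definition, that comparison would be biased against the Test lens.

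The cost is protocol wording and CRF completion guidance. Sites will record slightly more events, and reported AE rates will look slightly less favourable. No visit or procedure is added.
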